Assess the effectiveness of different efficacious strategies to decrease the rate of major wound complications following abdominal surgery among high-risk individuals.

Hypotheses

1. Among high-risk patients undergoing abdominal surgery, the use of “small-bites” closure as opposed to “large-bites” closure will increase the proportion of patients who are free of major, chronic wound complications at 1-year post-operative.
2. Among high-risk patients undergoing abdominal surgery, the biologic tissue reinforcement of the suture line as opposed to no reinforcement will increase the proportion of patients who are free of major, chronic wound complications at 1-year post-operative.

Methods

This is a single-institution, 2x2 factorial randomized controlled trial assessing the effectiveness of known efficacious treatments (“small-bites” and tissue reinforcement) among high-risk patients undergoing midline laparotomy or laparoscopic-assisted surgery. [19] Laparoscopic-assisted abdominal surgery is defined as any surgery requiring an open incision in addition to laparoscopy to insert a hand (hand-assisted laparoscopy) or specimen extraction site ≥ 3 cm in

length. This length is chosen because any smaller incision will likely be closed with interrupted sutures rather than running sutures.

Table 1: 2x2 Factorial Design for Prevention of Major, Chronic Wound Complication [19]

		Randomization 1	
		Small-Bites	(Current Care) Large-Bites
Randomization 2	Mesh	Small-Bites Mesh	Large-Bites Mesh
	(Current Care) No Mesh	Small-Bites No Mesh	Large-Bites No Mesh

A 2x2 factorial trial design is utilized because it is more efficient (can assess two interventions simultaneously) and mimics real-world practice (e.g. adoption bundle therapies, adoption of multi-faceted interventions). In addition, the 2x2 factorial design remains novel, particularly among surgical literature that can improve profile of studies performed with this approach.

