1 month	Routine care	Routine care Clinical exam Assessing: Hernia (clinical) Dindo-clavien complications Surgical site infections Patient centered outcomes (modified Activities Assessment Scale and Euroqol-5D)	\$0
1 year	Research follow-up	Clinical exam Assessing: Hernia (clinical and ultrasound) Dindo-clavien complications Patient centered outcomes (modified Activities Assessment Scale and Euroqol-5D)	\$10 gift card \$10 parking
3 years	Research follow-up	Clinical exam Assessing: Hernia (clinical and ultrasound) Dindo-clavien complications Patient centered outcomes (modified Activities Assessment Scale and Euroqol-5D)	\$20 gift card \$10 parking

A trained surgical clinician blinded to the treatment arms will collect outcomes. A blinded outcomes adjudication committee (non-participating members of the Ventral Hernia Outcomes Collaborative) will verify the primary outcome.

A Data Safety Monitoring Board of the Ventral Hernia Outcomes Collaborative will be developed. All major complications (Dindo-Clavien 3-5) including deaths, reoperations, mesh explantations, and enterocutaneous fistulas will be reviewed. No interim analysis will be planned as analysis of the primary outcome will weaken the strength of the results. Safety and stopping points will be determined based upon clinical judgment or greater than 50% rate of major complications.

Enrollment will occur prior to the operation either in the clinic (for elective cases) or on the day of surgery (for urgent or emergent cases). The randomization schema will be variable block randomization with blocks stratified by surgical approach (laparoscopic versus open): this is chosen not because there is belief that there will be a difference in outcomes, but because it is a different surgical approach and should be balanced. Allocation will occur at the time of abdominal closure by phone call to the study office.

Statistical analysis

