Based upon prior studies, it is estimated that the risk of a major, chronic wound complication in this population is at least 30% while either intervention would result in a decrease in relative risk by 30% (i.e. absolute risk reduction from 30% to 20%). The risk of complication at 1 year is the same with open or laparoscopic assisted surgery as shown in multiple prior studies. [1,2,26] Assuming an alpha of 0.05, beta of 0.20, and a dropout rate of 20%, a total of 192 300 patients would need to be enrolled and 154 patients randomized. Based upon our current surgical volume of nearly 6000 general surgical procedures performed each year and our track record of enrolling over 400 surgical patients in the past year for three other trials, we anticipate completing enrollment within one year. To encourage patient follow-up, all patients will be provided with up to a \$10 gift card at the one-year follow-up and \$20 at the three-year follow-up along with payments for their parking (\$10) at both one- and three-year visits. [23]

The primary outcome will be assessed as a categorical variable using a chi square test. In addition, analysis will be performed using a Cochran-Mantel-Haenszel method as well as a multivariate regression analysis accounting for the 2 randomizations and the stratification. Secondary outcomes will be assessed either chi-square or Kruskal-Wallis test.

Based upon traditional Frequentist assessment, if the effect size does not achieve “statistical significance” the conclusions risk being reported as a false negative. To address this potential risk, a more real-world, realistic analysis will be performed using a Bayesian analysis will also be performed. [24,25] The Bayesian models will take the same form as the Frequentist models and include the same covariates. Posterior point estimates, credible intervals, and probability of increase in proportion of patients without hernias or complications will be calculated. Similar models will be used for secondary outcomes. **If interactions or modifiers are identified, then this study will be underpowered and should be considered a pilot study to appropriately power future multi-center randomized controlled trials.**

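### The first-named test for the primary outcome ignores the randomization strata and no analysis is labelled primary; a CMH stratified by approach for each factor is a minor, low-cost improvement

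*Combined protocol and SAP*

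**What the plan says.** The Hypotheses section poses one two-level question per factor. The first is that small-bites rather than large-bites "closure will increase the proportion of patients who are free of major, chronic wound complications at 1-year post-operative". The second makes the same claim for biologic reinforcement against none.

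The randomization paragraph in Methods describes variable blocks, with "blocks stratified by surgical approach (laparoscopic versus open"). It adds that "this is chosen not because there is belief that there will be a difference in outcomes"; the stated purpose is balance.

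The Statistical analysis section states the premise that "The risk of complication at 1 year is the same with open or laparoscopic assisted surgery". For the primary outcome it then says "The primary outcome will be assessed as a categorical variable using a chi square test". The next sentence begins "In addition, analysis will be performed using a Cochran-Mantel-Haenszel method" and goes on to a "multivariate regression analysis accounting for the 2 randomizations and the stratification". A Bayesian analysis with the same model form and covariates follows.

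Three things are left open:
- which of these analyses is primary;
- whether the chi-square compares the two levels of each factor or all four arms;
- which strata the CMH uses. The phrase about the randomizations and the stratification can be read as belonging to the regression alone.

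**The concern.** When allocation is balanced within strata, the usual expectation is that the main analysis uses those strata. Here the test named first does not, and the analyses that could do so come second.

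Two things are at stake, both small. First, if approach is related to outcome, the unadjusted chi-square uses a variance that includes the difference between strata, although balanced allocation has already removed that difference from the treatment comparison. The test then rejects slightly too rarely. Second, several analyses of one outcome with no declared primary leave the choice of headline p-value open until the data are seen.

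**Working it through.** **Inputs from the Statistical analysis section.** Control risk is 30%, with an "absolute risk reduction from 30% to 20" percent (risk ratio 2/3). Alpha is 0.05, taken here as two-sided because sidedness is not stated. Power is 80% and dropout 20%. The enrolment figures 192 and 300 stand side by side, with 154 randomized.

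**Assumptions not in the documents.** Allocation is 1:1 per factor and balanced within approach. The approach effect and the share of open cases are varied.

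**The plan's own sample size.** Per level of a factor, n = [1.96 x sqrt(2 x 0.25 x 0.75) + 0.8416 x sqrt(0.21 + 0.16)]^2 / 0.10^2 = (1.2002 + 0.5119)^2 / 0.01, which rounds up to 294. That is 588 analysed and 588/0.8 = 735 enrolled, so the stated figures do not reproduce. Only the dropout arithmetic fits: 154/0.8 = 192.5 and 300 x 0.8 = 240. Two-sided power for 30% against 20% is about 30% at 154, 43% at 240 and 52% at 300. These three sizes are used below.

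**Size of the unadjusted test.** Let r be the within-stratum variance divided by the total variance. With balanced allocation the chi-square's actual size is about P(|Z| > 1.96/sqrt(r)). For a 50/50 split and 30% overall risk:
- Equal risks: r = 1, size 0.050.
- 20% and 40%: r = [(0.16 + 0.24)/2]/0.21 = 0.952, size 0.0446.
- 16.3% and 43.7% (odds ratio 4): r = 0.1912/0.21 = 0.911, size 0.040.

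The test errs toward too few rejections in every case.

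**Power by hand at N = 240, control risks 20% and 40%, risk ratio 2/3.** Risks averaged over the two levels are 16.7% and 33.3% in the strata and 25% overall. Total variance is 0.1875 and within-stratum variance is (0.1389 + 0.2222)/2 = 0.1806. Unadjusted z = 0.10/sqrt(0.1875 x 4/240) = 1.789. Stratified z = 1.789/sqrt(0.1806/0.1875) = 1.823. Approximate power is Phi(1.789 - 1.96) = 43.2% against Phi(1.823 - 1.96) = 44.5%, a gain of about 1.3 points.

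**Simulation.** 40,000 replicates per scenario, four equal arms, overall control risk held at 30%, no continuity correction in either test. The table gives power in percent, chi-square then CMH stratified by approach, with one factor effective and a 50/50 split. Cell rounding gives N = 152, 240 and 304.

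| Assumed approach effect (control risks) | N about 154 | N = 240 | N about 300 |
|---|---|---|---|
| None (30/30) | 29.7, 29.7 | 43.6, 43.6 | 52.5, 52.1 |
| Log odds ratio 1.0 (19.8/40.2) | 29.6, 30.9 | 43.5, 44.9 | 52.7, 53.8 |
| Odds ratio 4 (16.3/43.7) | 28.8, 31.2 | 43.2, 46.1 | 52.6, 55.3 |

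Other results:
- At log odds ratio 0.5 the change is -0.1 to +0.3 points.
- At log odds ratio 1.0 the gain is about 0.7 to 1.0 points with 70% open cases, and 0.5 to 1.0 with both factors effective.
- Type I error of the chi-square is 0.047-0.052 with equal risks, 0.042-0.047 at log odds ratio 1.0 and 0.038-0.045 at odds ratio 4. The CMH stays at 0.045-0.052 throughout.
- At N = 240, one factor effective and a 50/50 split, the mean 95% interval for the risk difference is 21.7 points wide unadjusted. Stratified, it is 21.6 (equal risks), 21.1 (log odds ratio 1.0) or 20.8 (odds ratio 4).

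Runs with 200,000 replicates agree with these figures. The 0.4-point loss with equal risks at N = 304 is largely an effect of discrete counts, since at N = 300 the loss is about 0.1. With random 20% dropout and equal risks the CMH loses about 0.2 points (43.5% to 43.3% starting from 300).

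**The case against.** The strongest reply is that nothing here is wrong. The chi-square is valid, and the regression already accounts for both randomizations and the stratification, so an adjusted result will be produced. The Bayesian models carry the same covariates. The benefit also needs an approach effect that the plan says does not exist. On the plan's premise, changing the test can cost a few tenths of a point. No required sample size, and probably no conclusion, would change.

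Most of this stands, and it limits the point to a minor one. It does not answer two things. Equal risk by approach is a premise, and the stratified test keeps its size near 0.05 whether or not it holds. The plan also still does not say which analysis is primary, which contrast the chi-square tests, or what the CMH strata are.

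A reader might infer more than the documents support:
- *The chi-square is invalid or inflates false positives.* It does not; any departure is conservative.
- *The plan ignores the stratification.* It does not; the regression includes it.
- *A CMH stratified by approach is already specified.* The CMH is planned, but its strata are not named; in a factorial trial they could be the other factor.
- *The change is free in every scenario.* Under equal risks it gives a small loss or nothing.

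**Conclusion.** The point holds as a minor improvement. The first-named test does not use the groups the trial randomizes by, and the primary analysis and the CMH strata are unstated.

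Under the plan's premise of equal risk by approach, the change in power is about -0.4 to 0 points. If approach matters at an assumed log odds ratio of 1.0, the gain is about 0.5 to 1.5 points and the size of the test returns from about 0.042-0.047 to about 0.05. Gains of 2 to 3 points need an assumed odds ratio of 4 with one factor effective and an even split. Neither approach effect has a source in the documents.

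It would be wrong to read this as a remedy for low power. Power is about 30% to 52% against a planned 80%, and no choice between these two tests closes that gap. The stronger reasons to act are that the analysis would follow the randomization and that one primary test per factor would be fixed in advance.

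**What to change.** In the Statistical analysis section, state for each factor separately (small against large bites; mesh against no mesh):
- The primary test is the CMH on that factor's two levels, stratified by surgical approach. The other factor need not be a stratum; adding it changes the gains by at most about 0.6 points.
- The estimate is an approach-adjusted risk difference or risk ratio with a 95% confidence interval, so that it can be read against the planned 30% and 20%.
- The unadjusted chi-square, the regression and the Bayesian analysis are supportive for the primary outcome.

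The cost is a few sentences. A CMH is already planned and approach is recorded for randomization, so no patients, visits or alpha are spent. The possible price is a loss of up to about 0.4 power points if approach has no effect. The 192, 300 and 154 figures, and the sample size itself, need separate attention.

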Tissue Reinforcement of Incisional Closure Among High Risk Patients

NCT03148496

[figure not shown]
Version Date: 03/06/2020

IRB NUMBER: HSC-MS-17-0063
IRB APPROVAL DATE: 03/06/2020

Tissue Reinforcement of Incisional Closure Among High Risk Patients

[name], [name], [name]
Mentor: [name]

Background

One-third of all individuals will undergo abdominal surgery in their lifetime. [1,2] Following abdominal surgery, 30% of patients will suffer a major chronic complication with their wound closure in the first post-operative year. This may include significant wound infections, open wounds, fluid collections, fascial dehiscence, or incisional hernia. These complications not only have a substantial impact on the health care system (cost and chronic disease) and the hospital (cost and space), but most importantly have a substantial impact on the patient. Major chronic wound complications adversely impact patient quality of life and function. [3-6]

Patients at greatest risk for major wound complications include comorbid patients such those who are overweight or obese, currently smoke or have COPD, are immunosuppressed, are malnourished, or who have evidence of contamination (wound classes 2-4). Among these patients, the risk of developing a major wound complication ranges from 30%-80%. [1,2,7,8,9]

Potential methods to reduce major wound complications include utilizing specific suturing techniques or reinforcing the incision line. Suturing technique of small-bites (0.5x0.5 cm bites) as opposed to large bites (1.0x1.0 cm bites) has been shown to be efficacious in European populations with a typical body mass index of 20-25 kg/m². [10-12] Tissue reinforcement has been shown to decrease rates of major wound complications in small randomized controlled trials. [13-18]

However, the lack of widespread adoption of these practices may be due to issues of generalizability including strict inclusion criteria, careful patient selection, and small study size. For example, the generalizability of small bites to an overweight population (mean BMI in the United States is 28 kg/m²) as opposed to a normal-weight population are unclear. [10-12] The use of synthetic materials in comorbid patients or complex settings may risk major wound complications such as prosthetic infection. Biologic materials have been shown to be effective in decreasing major wound complications but in different settings. [13-19]

Specific Aims

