Inclusion criteria will include all high-risk patients undergoing laparotomy or laparoscopic-assisted abdominal surgery. High-risk patients will include (1) all overweight patients, (2) current smokers, (3) those who are immunosuppressed, (4) those who are malnourished, or (5) those who are undergoing a contaminated case. Overweight is defined as $BMI \geq 25 \text{ kg/m}^2$. Current smoker is any patient who routinely smokes within the past month. Immunocompetent is any patient who has or will receive immunosuppressive medications or drugs within 3 months of surgery. Malnourished is defined as albumin $<3.5 \text{ g/dL}$. Contamination is defined as Center for Disease Control wound classification 2 or 3. [20]

Exclusion criteria include (1) patients unlikely to follow-up in a year (e.g. no phone or lives out of state), (2) patients unlikely to survive more than 2 years based upon surgeon judgment (e.g. metastatic cancer, end-stage cirrhosis), (3) patients where the clinician would not place prosthetic (e.g. pregnant patient, pediatric patient during growth stage), (4) patients on full anticoagulation treatment or (5) patient has a planned second surgery within the next year (e.g. ostomy reversal).

Current care for wound closure includes a 1x1 cm closure using a slowly absorbable, running suture (0 polydioxanone). Surveys among surgeons have identified that the vast majority of United States surgeons and surgeons at our institution perform abdominal closure in this technique. "Small-bites" will be performed using a 0.5x0.5 cm closure using a slowly absorbable running suture (2-0 polydioxanone). Mesh placed will be a biologic mesh, (porcine acellular dermal matrix) and will be fenestrated with a scalpel. Preperitoneal space will be chosen for all midline incisions where preperitoneal space can be safely and easily developed (open, lower midline incisions). Underlay will be chosen for all off midline (e.g. stoma site incision) where laparoscopic fixation will be more efficient.

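### A small, cheap gain in precision is open: the planned primary-outcome regression adjusts for surgical approach but for none of the baseline risk factors that define the population

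*Combined protocol and SAP*

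**What the plan says.** In the combined protocol and SAP, the Statistical analysis section states: "The primary outcome will be assessed as a categorical variable using a chi square test". It then adds a Cochran-Mantel-Haenszel analysis and a "multivariate regression analysis accounting for the 2 randomizations and the stratification". The Bayesian models are to have the same form and covariates.

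The only stratification factor is laparoscopic versus open surgery (Methods, randomization paragraph). Of that choice the plan says "this is chosen not because there is belief that there will be a difference in outcomes". The Statistical analysis section adds: "The risk of complication at 1 year is the same with open or laparoscopic assisted surgery".

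The Background describes who is at risk: "Patients at greatest risk for major wound complications include comorbid patients such those who are overweight or obese, currently smoke", and it continues with COPD, immunosuppression, malnutrition and contamination. It puts the risk of a major wound complication among such patients at 30% to 80%. The inclusion criteria in Methods use overweight, smoking, immunosuppression, malnutrition and contamination, and meeting any one is enough for entry. None of these is named as a covariate in any analysis.

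**The concern.** A baseline covariate improves the precision of a treatment comparison only if it predicts the outcome. The plan adjusts for one variable that it expects not to predict the outcome, and leaves out those it treats as the main drivers of risk. Randomization protects the comparison either way, so only efficiency is at stake. That matters a little here because power per hypothesis is low and the extra precision costs almost nothing.

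There is also a question of timing. If covariates are added after unblinding, the adjusted and unadjusted analyses can disagree, and the choice between them would then be open to the result. A list fixed in advance removes that.

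**Working it through.** **1. Numbers of patients.** The plan prints 192 and 300 enrolled side by side, 154 randomized, and 20% dropout. 192 × 0.8 = 153.6, which gives 154; 300 × 0.8 = 240. I take 154 and 240 as evaluable, and assume 1:1 allocation on each factor and a two-sided 5% test. The plan's 80% power does not reproduce at either number. With 30% v 20%, n per side = (1.96·√(2·0.25·0.75) + 0.842·√(0.21 + 0.16))² / 0.10² ≈ 293.2, so 294 per side and 588 in all. That is a separate and larger problem.

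**2. Starting power on a factor's margin.** Power = Φ[(d − 1.96·SE₀)/SE₁], with N/2 per side, SE₀ pooled and SE₁ unpooled.
- Only the tested intervention works: 30% v 20%, d = 0.10. Power is 29.8% (N=154) and 43.2% (N=240).
- Both work and combine on the odds scale (an assumption): OR = 0.25/0.4286 = 0.583. The odds with both are 0.25 × 0.583 = 0.146, a risk of 12.7%. The margins are (30 + 20)/2 = 25.0% v (20 + 12.7)/2 = 16.4%. Power is 26.1% (N=154) and 37.8% (N=240).
- Expected events in the second case: 154 × 0.207 ≈ 32 and 240 × 0.207 ≈ 50.

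**3. How prognostic are the factors?** The documents do not say. The only hint is the Background range: (0.8/0.2)/(0.3/0.7) = 9.33, which is 9.33^(1/3) = 2.11 per factor over three factors, or 9.33^(1/4) = 1.75 per step from one criterion to five. This assumes that the range reflects differences between patients, so I show a range of odds ratios.

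**4. Dichotomized factors.** The simulation used 8,000 trials per scenario, logistic models, both interventions active, blocks stratified by approach, and no approach effect. All five criteria were prognostic with a common odds ratio. Assumed prevalences were BMI ≥25 70%, smoker 25%, contaminated 40%, immunosuppressed 10% and malnourished 20%. The added covariates are BMI ≥25, smoking and contamination.

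| N | OR per factor | Chi-square | Planned regression | Plus 3 factors |
|---|---|---|---|---|
| 154 | 1.5 | 26.8% | 26.5% | 27.3% |
| 154 | 2.0 | 26.9% | 26.6% | 27.1% |
| 154 | 2.5 | 25.9% | 25.8% | 27.8% |
| 240 | 1.5 | 39.2% | 39.1% | 39.6% |
| 240 | 2.0 | 39.5% | 39.5% | 40.1% |
| 240 | 2.5 | 38.5% | 38.5% | 40.4% |

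A rerun at OR 1.5 to 2.1 gave 0.2 to 1.2 points over the chi-square, and about −1 to +1 at equal type I error. Gains of 3 points or more needed OR 4.0.

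**5. BMI kept continuous.** A cut at 25 puts everyone from mildly overweight to severely obese in one group, and the Background gives a United States mean of 28. With continuous BMI (OR 1.5 to 2 per 5 kg/m²) plus smoking and wound class (OR 1.75 to 2.1), all assumed, the gain is about 1 to 4 points. At equal type I error it is 0.3 to 4.5. Type I error was 4.6% to 5.5%.

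**6. Cross-check.** A separate simulation (4,000 trials, other factor inactive) used a normal risk score with SD 0.5 or 0.8 on the logit scale, which is an odds ratio per SD of e^0.5 = 1.65 or e^0.8 = 2.23. Power without and with the score was 30.6% and 31.6%, then 29.1% and 32.4%, at N=154. At N=240 it was 43.2% and 43.9%, then 42.6% and 46.0%. The gains are 0.7 to 3.4 points, in line with step 5.

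**7. Disagreement between tests.** Once three factors are added, the adjusted regression and the chi-square reach different verdicts in roughly 4% to 9% of trials. Among the methods already planned it is about 1% to 2%.

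**The case against.** The strongest case against is that this is an analyst's preference with almost no return. With dichotomized factors at plausible odds ratios the gain is within about one point and vanishes at equal type I error. That stands. It is why BMI should be continuous and why the point is only optional.

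The Background range is also a weak anchor. It may reflect differences between cited sources. It covers COPD and wound classes 2 to 4, whereas the inclusion criteria omit COPD and stop at class 3. It concerns major wound complications in general, whereas the wound and infection components of the primary outcome must persist at one year. If patients' risks truly ran from 30% to 80%, the control mean would exceed the 30% used in the simulations. All of this stands, so the gain is given as a range under assumed odds ratios.

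A reader might infer that adjusting for approach is a mistake because approach is not prognostic. The documents do not support that: approach stratifies the randomization, and keeping it in the model is correct practice whatever its prognostic value.

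A reader might also infer that the plan leaves the deciding test wholly open. The chi-square is named first and the others come in addition, which suggests an order. Naming a deciding analysis matters mainly once covariates are added.

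**Conclusion.** The omission is as described, and it is a matter of efficiency only. The planned analyses are not biased by it. The expected gain is about 0 to 1 power point with dichotomized factors at OR 1.5 to 2.1, and about 1 to 4 points with continuous BMI under the odds ratios assumed above. With weak factors at N=154 it is about nil. If only the tested intervention works, the starting power is the higher pair in step 2.

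Two stronger readings should be resisted. One is that the Background range proves the factors strongly prognostic, so that the gain would be large. Larger gains can be produced (6.2 points at N=240 with a risk-score SD of 1.0, from 43.4% to 49.6%), but nothing in the documents supports that strength. The other is that adjustment could rescue the power: it leaves every scenario at the supported strengths far below 80%.

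**What to change.** Before unblinding, amend the Statistical analysis section as follows.
- Keep both randomizations and surgical approach in the planned regression. Add two, at most three, prespecified covariates measured before allocation: BMI as a continuous variable, smoking, and wound class if it is recorded before the allocation call at closure.
- Carry the same covariates into the Bayesian models.
- State that this regression decides each hypothesis on its factor's margin, through the treatment coefficient. Keep the chi-square and Cochran-Mantel-Haenszel analyses as supportive.
- Report a standardized risk difference with 95% CI, on the scale of the plan's 30% to 20%. Use it for size of effect, since its own test ran at 4.8% to 6.0% type I error in the simulations.
- Give a simple rule for missing covariates.

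The cost is SAP wording and a check of the data. No baseline data schedule is given, and because any one criterion suffices for entry, a factor such as albumin may not be recorded for everyone. With about 32 events at N=154, the list must stay short.
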